2.2 Secondary estimands

None.

3 Study design

This will be a multicenter, interventional, open-label, and prospective single-arm study to evaluate the effect of ARNI on VAs in approximately 219 HFrEF patients receiving ICD or CRT-D in China (Figure 3-1).

Figure 3-1 Study design

Abbreviations: ACEI = Angiotensin-converting enzyme inhibitor; ARB = Angiotensin receptor blockers; ARNI = Angiotensin receptor neprilysin inhibitor; EOS = End of Study Note:

- *Data collection at Baseline(0), Month 1, Month 3, Month 6, Month 7, Month 9, and Month 12 according to the evaluation schedule.
- Dosage and titration plan of ACEI/ARB and ARNI treatments will be according to investigator's discretion and product label (Please refer to Table 6-2 and Table 6-3).
- 36-hr washout period is not needed for patients using ARB.

Page 23 of 63 Protocol No. CLCZ696BCN04

Patients will be informed about the study purpose and asked to sign an informed consent form. Demographics, etiology of HF, comorbidities, New York Heart Association (NYHA) class, baseline laboratory, electrocardiogram, echocardiogram, medical treatment, and implanted device (ICD or CRT-D) type and date will be collected at Baseline. Device data of patients will be collected for 12 months. Once the device is implanted, ACEI/ARB will be given to the patient. Dosage of ACEI/ARB will be based on investigator's discretion and up-titrated after 2-4 weeks to the maximum dosage the patients can tolerate and according to product label.

After 6 months, patients using ACEI need to undergo a 36-hr washout period (36-hr washout period is not needed for patients using ARB at month 6). Patients will then receive ARNI (sponsored by Novartis only for this study) while the dosage of ARNI will be according to investigator's discretion and up titrated to the maximum dosage the patient can tolerate or 200 mg bid as per guideline. The recommended starting dose of ARNI is presented in Table 6-3.

All patients will be followed up for 6 months for each treatment. After patients finalize the trial, the investigator will evaluate all patients and produce a report.

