6.1.5 Treatment duration

The planned duration of treatment for ACEI/ARB and ARNI is 6 months each. During the ACEI/ARB period, the drug choice and dosage are at the discretion of the physician. The EOS will occur when the pre-specified number of patients completed the 12 months treatment. Patients may be discontinued earlier due to unacceptable toxicity and/or treatment is discontinued at the discretion of the investigator or the patient. For patients who in the opinion of the investigator are still deriving clinical benefit from ARNI, every effort will be made to continue provision of study treatment.

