9.3 Study completion and post-study treatment

Study completion is defined as when the last patient finishes their Study Completion visit and any repeat assessments associated with this visit have been documented and followed-up appropriately by the Investigator or, in the event of an early study termination decision, the date of that decision (e.g. Each patient will be required to complete the study in its entirety and thereafter no further study treatment will be made available to them).

All treated patients should have a safety follow-up call conducted 30 days after last administration of study treatment. The information collected is kept as source documentation. All SAEs reported during this time period must be reported as described in Section 10.1.3. Documentation of attempts to contact the patient should be recorded in the source documentation.

Continuing care should be provided by the investigator and/or referring physician based on patient availability for follow-up. This care may include:

Enrollment in an extension study, if any

10 Safety monitoring and reporting

The definitions of adverse events (AEs) and serious adverse events (SAEs) can be found in Section 10.1.

The Investigator and any qualified designees are responsible for detecting, documenting, and recording events that meet the definition of an AE or SAE and remain responsible for following up.

The method of recording, evaluating, and assessing causality of AEs and SAEs and the procedures for completing and transmitting SAE reports are provided in Section 10.1.3.

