Conditions that were already present at the time of informed consent should be recorded in medical history of the patient.

Adverse events (including lab abnormalities that constitute AEs) should be described using a diagnosis whenever possible, rather than individual underlying signs and symptoms.

Adverse event monitoring should be continued for at least 30 days following the last dose of study treatment.

Once an AE is detected, it must be followed until its resolution or until it is judged to be not recovered/not resolved (e.g., continuing at the end of the study), and assessment must be made at each visit (or more frequently, if necessary) of any changes in severity, the suspected relationship to the interventions required to treat it, and the outcome.

Information about adverse drug reactions for the investigational drug can be found in the product label.

Abnormal laboratory values or test results constitute AEs only if they fulfill at least one of the following criteria:

- they induce clinical signs or symptoms
- they are considered clinically significant
- they require therapy

Clinically significant abnormal laboratory values or test results must be identified through a review of values outside of normal ranges/clinically notable ranges, significant changes from baseline or the previous visit, or values which are considered to be non-typical in participant with the underlying disease. Alert ranges for laboratory and other test abnormalities are included in Appendix 1.

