12.5.3 Safety endpoints

For all safety analyses, the SAF will be used and there will be no formal statistical inference analysis. All listings and tables will be presented by treatment group.

Safety summaries (tables and figures) include only data from the on-treatment period with the exception of baseline data which will also be summarized where appropriate (e.g. change from baseline summaries). In addition, a separate summary for death including on treatment and post treatment deaths will be provided. In particular, summary tables for AEs will summarize only on-treatment events, with a start date during the on-treatment period (treatment-emergent AEs).

Adverse events

All information obtained on AE will be displayed by treatment group and patient.

The number (and percentage) of patients with treatment-emergent AE (events started after the first dose of study medication or events present prior to start of double-blind treatment but increased in severity based on preferred term) will be summarized by treatment, primary system organ class, preferred term and maximum severity.

Separate summaries will be provided for study medication related AE, death, SAE, other significant AE leading to discontinuation and AE leading to dose adjustment.

The number and proportion of patients with AE as described in Section 10.1 will be summarized by treatment.

A patient with multiple AE within a primary system organ class is only counted once toward the total of the primary system organ class.

Adverse events which will be counted for a specific treatment period are those which are treatment-emergent. These events are those with an onset after the start of the treatment period, or which were present prior to the start of the treatment period but increased in severity, changed from being not suspected to being suspected of study drug relationship, or developed into SAEs after the start of the treatment period.

Vital signs

All vital signs data (see Section 8.4.2) will be listed by treatment group, patient, and visit/time and if ranges are available, abnormalities (and relevant orthostatic changes) will be flagged. Summary statistics will be provided by treatment and visit/time.

Clinical laboratory evaluations

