first ACEI/ARB administration and before ARNI administration. If the subject has not taken ARNI, TEAEs in the ACEI/ARB treatment group refer to adverse events that occur from the subject's first ACEI/ARB administration to 30 days after the subject's last ACEI/ARB administration. TEAEs in the ARNI treatment group refer to adverse events that occur from the subject's first ARNI administration to 30 days after the subject's last ARNI administration.

Pre-treatment events

Pre-treatment adverse events are defined as those that occur after the signing of the informed consent form and before the day of first administration of the investigational drug.

Drug-related adverse events (adverse reactions)

An adverse drug reaction (ADR) is a toxic and adverse reaction to a drug. An ADR indicates that there is at least a reasonable likelihood of a causality between the drug and an adverse event. In this study, the causality between an adverse event and the investigational drug is judged according to "suspected" and "not suspected". "Suspected" adverse events are judged as adverse reactions. If the event is due to lack of efficacy or progression of underlying illness (i.e. progression of the study indication), the assessment of causality will usually be 'Not suspected.'

AEs leading to death

Adverse events leading to death will be recorded by the investigator on the CRF Adverse Events Form. In addition, there is a specialized CRF to record deaths.

Serious adverse events

SAEs will be collected between time patient signs ICF until 30 days after the patient has discontinued or stopped study treatment. An SAE is defined as any adverse event [appearance of (or worsening of any pre-existing)] undesirable sign(s), symptom(s), or medical conditions(s) which meets any one of the following criteria:

- fatal
- life-threatening

Life-threatening in the context of an SAE refers to a reaction in which the patient is at risk of death at the time of the reaction; it does not refer to a reaction that hypothetically might have caused death if it is more severe.

- results in persistent or significant disability/incapacity
- constitutes a congenital anomaly or birth defect
- requires inpatient hospitalization or prolongation of existing hospitalization, unless hospitalization is for:
 - routine treatment or monitoring of the studied indication, not associated with any deterioration in condition.

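### SAP 4.2.2 follows switching patients about 30 days longer for adverse events on ARNI than on ACEI/ARB, and SAP 7.5.2 sets unadjusted percentages side by side

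*SAP*

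**What the plan says.** SAP 4.2.2 assigns treatment-emergent adverse events (TEAEs) to a treatment period under three end rules.

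- ARNI: "adverse events that occur from the subject's first ARNI administration to 30 days after the subject's last ARNI administration".
- ACEI/ARB, patients who switch: events after the "first ACEI/ARB administration and before ARNI administration", so there is no tail.
- ACEI/ARB, patients who never switch: "If the subject has not taken ARNI, TEAEs in the ACEI/ARB treatment group refer to adverse events" from first dose to 30 days after last dose, so there is a tail.

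Protocol 6.1.5 sets the treatment length: "The planned duration of treatment for ACEI/ARB and ARNI is 6 months each". Events after the last dose are meant to be observed. Protocol 10.1.1 says "Adverse event monitoring should be continued for at least 30 days following the last dose of study treatment", and Protocol 9.3 adds "All treated patients should have a safety follow-up call conducted 30 days after last administration of study treatment".

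SAP 7.5.2 then tabulates the number and percentage of patients with TEAEs, serious, drug-related and fatal events, and events leading to withdrawal, by treatment group. SAP 7.5.1 summarises exposure duration separately. Neither section plans an event rate per unit of time.

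Protocol 12.5.3 says "Safety summaries (tables and figures) include only data from the on-treatment period" (apart from baseline data), and SAP 7.5.2 likewise restricts the safety summary to data during treatment. Neither says when that period ends.

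**The concern.** The by-treatment percentages are this single-arm trial's only side-by-side view of safety on the two drugs. If one column collects events for a month longer, its percentages rise even when the drugs are equally safe, and nothing in the tables lets a reader remove that. Closing the ACEI/ARB window at the switch also books any late-emerging ACEI/ARB event to ARNI, which acts in the same direction.

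The SAP accepts the principle elsewhere: SAP 7.4.2 puts device counts on a daily basis before analysing changes, because collection periods differ in length. Adverse events get no such treatment.

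A second, smaller matter is that a programmer could build the ARNI tables with or without the 30 days after last dose, depending on whether SAP 4.2.2 or the on-treatment wording of SAP 7.5.2 is followed.

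**Working it through.** The documents give no expected adverse event incidence, so there is no planned figure to reproduce. The incidences below are illustrative.

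**Inputs**
- Treatment length: 6 months per period (Protocol 6.1.5), taken as 6 × 365.25/12 = 182.6 days.
- Tail: 30 days (SAP 4.2.2).
- Washout: Protocol section 3 says "After 6 months, patients using ACEI need to undergo a 36-hr washout period". This is 1.5 days for ACEI users and falls in the ACEI/ARB window.
- Visit tolerance: ± 2 weeks at Month 6 (Protocol Table 8-1).
- Dropout: 20% (SAP 3.2.1), used as an upper value for patients who never switch.

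**Step 1: window lengths for a patient who completes both periods**
- ACEI/ARB: 182.6 days, or 182.6 + 1.5 = 184.1 with washout.
- ARNI: 182.6 + 30 = 212.6 days.
- Ratio: 212.6/182.6 = 1.16, or 212.6/184.1 = 1.15 with washout.

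**Step 2: effect on percentages.** Assume the same constant hazard in both periods and full capture. If p is the ACEI/ARB incidence, the ARNI incidence is 1 − (1 − p)^(212.6/182.6).

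| ACEI/ARB | ARNI | Relative excess |
|---|---|---|
| 5% | 5.8% | 16% |
| 10% | 11.5% | 15% |
| 30% | 34.0% | 13% |
| 50% | 55.4% | 11% |

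**Step 3: does the tail for non-switchers restore balance?** Let a fraction f never switch and stop ACEI/ARB on day t. The mean ACEI/ARB window is (1 − f) × 184.1 + f × (t + 30). Assume f = 0.10 to 0.20 and t = 30 to 150.
- f = 0.10, t = 150: 165.7 + 18 = 183.7 days; ratio 212.6/183.7 = 1.16.
- f = 0.20, t = 30: 147.3 + 12 = 159.3 days; ratio 212.6/159.3 = 1.33.

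Balance is not restored, because these patients stop early. The calculation lets every ARNI starter complete; early stopping on ARNI would lower the ratio. A person-time rate deals with both.

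**Step 4: other assumptions** (ACEI/ARB window 184.1 days in the first two)
- Hazard k times higher in the first 30 days of each period. The effective lengths are 30k + 154.1 and 30k + 182.6. For k = 2: 242.6/214.1 = 1.13, so 10% becomes 11.3% and 30% becomes 33.2%. For k = 4: 302.6/274.1 = 1.10, so 10% becomes 11.0% and 30% becomes 32.5%. The relative excess is about 8-13%.
- Half of the tail events captured: (182.6 + 15)/184.1 = 1.07.
- Switch 2 weeks late, Month 12 fixed: 198.6/196.6 = 1.01. Two weeks early: 226.6/168.6 = 1.34.

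**Step 5: after the change.** With the tail out of the comparative table, the windows are 182.6 to 184.1 days on ACEI/ARB and 182.6 on ARNI, a ratio of 0.99 to 1.00. A rate over each window's own person-time gives 1.00 under equal hazard.

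**The case against.** A reader might infer that the safety comparison is, overall, biased against ARNI. The documents do not support that. Only patients who got through the ACEI/ARB period receive ARNI, and ACEI/ARB starts soon after implantation (inclusion requires implantation within 2 weeks). An event already present when ARNI starts counts for ARNI only if it worsens, becomes suspected or becomes serious. Each of these may push the other way. This objection stands: only the effect of the window taken alone has a known direction.

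A reader might also infer that SAP 4.2.2 contradicts Protocol 12.5.3. The protocol equates on-treatment events with treatment-emergent ones and gives no end date, so the SAP's 30 days can be read as supplying the missing definition. What remains is unclear wording.

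Nor can one say that patients take other therapy during the tail. Protocol 6.1.5 speaks of efforts to continue study treatment for those still benefiting, while Protocol 9.3 speaks of none being available after completion.

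Capture in the tail may be incomplete. The last scheduled assessment is Visit 7, contact after that is a call kept as source documentation, and Protocol 9.3 expressly requires reporting only of serious events. A constant hazard is also least credible for drug-related events if patients are off drug. Both points stand and are why a range is given.

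Finally, closing one window when the next opens assigns each event to one period only, and Protocol 12.5.3 plans no inference on safety. Both are true; neither explains why the comparative ARNI window needs a tail.

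**Conclusion.** The concern holds in a limited form. For patients who complete both periods as planned, the ARNI window is about 30 days, or 16%, longer, and no planned table corrects for it. Under equal constant hazard and full capture this alone adds about 1.5 percentage points at 10% and 5.4 at 50%. It shrinks with early-peaking hazards or incomplete capture, nearly vanishes if the switch comes two weeks late with Month 12 fixed, and grows if the switch comes early. The 30-day tail for non-switchers does not offset it under the assumptions tried. The hazard shapes, capture fraction, share of non-switchers and their stopping times are assumptions.

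The net direction of the ARNI versus ACEI/ARB safety comparison is unknown. The tables are descriptive and no efficacy result is affected. This is an inexpensive improvement that removes an avoidable imbalance, and it does not threaten the trial's conclusions.

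**What to change.** In SAP 4.2.2 and 7.5.2:

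1. For the between-period TEAE tables, count ACEI/ARB events from the first ACEI/ARB dose to the first ARNI dose, or to the last ACEI/ARB dose if the patient never switched. The washout stays in this window. Count ARNI events from first to last ARNI dose.
2. Show events in the 30 days after last dose in a separate row, for ARNI and for ACEI/ARB patients who never switched, so that no event is lost.
3. Add patients with events per 100 patient-months at risk, using each window's own person-time up to the first event.
4. State in SAP 7.5.2 whether data during treatment include the 30-day tail, so that it agrees with SAP 4.2.2 and Protocol 12.5.3.

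The cost is SAP wording, a few more table rows and a person-time derivation. The dosing dates are already collected in the CRF (SAP 4.2.1), so no new data are needed.

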4.2.3 Laboratory test

It will be done at the study site according to the laboratory requirements and standards of the study site. Laboratory tests include hematology, blood biochemistry, kidney function, biomarkers, and pregnancy tests.

Category	Items
Hematology	Red blood cells count, white blood cells count, platelet count,
	hemoglobin, hematocrit, and WBC differential
Blood chemistry	Potassium, creatinine, glucose, sodium, chloride, calcium, blood urea
	nitrogen, total bilirubin, fractionated bilirubin (if total bilirubin >2x
	ULN), aspartate aminotransferase (AST), alanine aminotransferase
	(ALT), alkaline phosphatase, total protein, albumin, uric acid, cholesterol,
	triglyceride, low density lipoprotein, high density lipoprotein, eGFR,

	glycosylated haemoglobin	
Kidney function	Serum creatinine	
Biomarkers	NT-proBNP	
Pregnancy test	Serum/urine pregnancy test	

4.2.4 12-lead ECG examination

The CRF collects the test results of heart rate, RR interval, PR interval, QT interval, QRS interval and QTcF interval and their clinical assessments (normal, abnormal with no clinical significance, abnormal with clinical significance).

4.2.5 Holter

The CRF collects the results of ventricular premature beat, atrial premature beat, mean heart rate, ventricular tachycardia, and atrial tachycardia.

4.2.6 Echocardiography

The CRF collects the test results of left ventricular ejection fraction (LVEF) (%) and left ventricular end-diastolic diameter (LVEDD) (mm).

4.2.7 Vital signs

The CRF collects subjects' mean systolic blood pressure, mean diastolic blood pressure, body temperature, heart rate, and respiratory rate measurements and their clinical assessments (normal, abnormal with no clinical significance, abnormal with clinical significance).

4.2.8 Physical examination

The CRF collects subjects' skin, neck, eyes, ears, nose, throat, lungs, heart, abdomen, back, lymph nodes, limbs, blood vessels, nervous system, rectum, external genitalia, breasts, pelvis, and other examinations and their clinical assessments (normal, abnormal with no clinical significance, abnormal with clinical significance).

4.2.9 Pregnancy test (only for women of childbearing)

The CRF collects subjects' (women of reproductive age) blood and urine pregnancy test results.

4.3 Demographics and Disease Characteristics

The CRF collects subjects' date of birth, age, gender, ethnicity, height, weight, and BMI.

The CRF collects current and past medical history, and history of heart failure.

4.4 Past and concomitant medication and concurrent treatment

The CRF collects the drug name, total daily dose and unit, frequency of administration, route of administration, start date, end date, ongoing or not, and indication for prior and concomitant medications.

The CRF collects the name, start date, end date, ongoing or not, and indication of concomitant treatments (non-drug concomitant treatments, including surgery).

4.5 **Protocol Deviation and Medication Compliance**

Protocol deviations will be recorded by the clinical monitor.

Medication compliance for ACEI/ARB and ARNI is defined as: total actual dose/total planned dose *100%. Overall medication compliance for ACEI/ARB and ARNI will be summarized.

5. Statistical Hypotheses

For details, see section 7.4 Efficacy Analysis.

6. Analysis Datasets

The analysis data sets of this study are as follows.

Screened set

It includes all subjects who have signed the informed consent form.

Safety Analysis Set, SS

It includes all subjects who had received at least one dose of study treatment. Analyses will be performed according to the study treatment received. The safety analysis set will be used for all analyses except the efficacy analysis.

Efficacy Analysis Set

It includes SS subjects who have received ARNI at least once and completed 12 months of complete treatment and follow-up or who have early withdrawn from the study after receiving ARNI at least once. The efficacy analysis set will be used as the primary population to analyze the efficacy variables.

Per Protocol Set, PPS

It includes subjects in efficacy analysis set who had no major protocol violations, and the PP population will be used for efficacy analysis.

7. Statistical Methods

